8.3.19.5.2 Food Diary Compliance

Food diary compliance is calculated as the total count of 'Yes, with evening meal' to taking a meal with the study drug, using the same methods of study drug diary compliance.

8.3.19.5.3 Glucocorticoid Diary Compliance

Total GC diary compliance is calculated as the total count of number of 'Yes' or 'Took Stress Dosing' responses to taking GC as directed and number of stress dosing days, divided by (LASTDAY – FIRSTDAY+ 1 day), where LASTDAY is the date of last dose, and FIRSTDAY is the date of first dose.

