4.1.4.4 Stress Dosing of Glucocorticoid

During times of clinically significant physical stress such as intercurrent illness with fever, surgical procedures, or significant trauma, subjects may take extra GC (in the form of HC) consistent with the “sick day guidelines” for prevention of adrenal crisis shown in [Table 2](#) ([Bornstein 2016](#)). Sites may employ variations on these guidelines, consulting with the Medical Monitor, if possible, in non-urgent situations. The Sponsor will provide all subjects with oral HC for the purposes of stress dosing ([Section 6.2.2](#)). For subjects who are not taking HC as their background GC regimen, the stress dose of HC should be estimated based on the relative potencies of GCs specified in [Table 1](#).

The stress doses recommended in [Table 2](#) are meant to *replace* a subject’s usual daily GC dose; they are NOT taken *in addition* to the subject’s usual daily GC dose. When taking the stress dose orally, the subject should take the entire stress dose using HC tablets from the bottle provided by the Sponsor. Daily replacement dosing from the subject’s or Sponsor-provided GCs should be temporarily held during stress dosing and reinstated as soon as the stress dosing period ends.

While all GC stress doses should be entered into the EDC, changes to usual daily GC dose only need to be entered into EDC when there is a definitive long-term, chronic alteration in the usual daily GC dosing regimen.

Table 2. Sick Day Guidelines for Stress Dosing of Hydrocortisone

Condition	Stress Dosing of Hydrocortisone
Home management of fever >38 °C (>100.4 °F) or illness requiring bed rest, when requiring antibiotics for an infection, or before undergoing a minor outpatient procedure (eg, dental work)	
 Approximately double the routine oral GC dose (and give as HC) until recovery (usually 2 to 3 days) For fever >39 °C (102.2 °F) only, approximately triple the routine oral GC dose (and give as HC) until recovery (usually 2 to 3 days)¹ Increase consumption of electrolyte-containing fluids and simple and complex carbohydrates (El-Maouche 2018), as tolerated
Unable to tolerate oral medication due to gastroenteritis or trauma	
 HC 100 mg IM or SC
Minor to moderate surgical stress	
 HC 25 to 75 mg/24 hours (usually 1 to 2 days)

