7.3 Per-Protocol Analysis Set

The Per-Protocol (PP) Analysis Set for each part of the Treatment Period will include all eligible subjects who have no major protocol deviations that would affect the analysis of efficacy data, defined prior to the database lock as the following:

- Subject did not meet efficacy-based inclusion criteria (hormone levels, GC regimen)

- Subject met efficacy-based exclusion criteria (inadequate adherence to GC regimen, night-shift worker)
- Subject's adherence to study drug or the subject-specific GC regimen, determined by pill count and diary data compliance, was < 80% over the Treatment Period
- Subjects having laboratory data specifically hormone levels during stress dosing periods instead of waiting 5 days per protocol.

The PP population will be used for supportive analyses of the Primary and Secondary Efficacy Endpoints only.

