8.3.20.4 Stress Event

A stress event is defined as an entry in the diary indicating a stress dose was taken or a record in the CM eCRF if the stress dosing was not recorded in the diary in a timely manner. Consecutive days of stress dosing are counted as a single stress event.

8.3.20.5 Cumulative GC Dose at Week 24

The cumulative GC dose from Study Day 1 to Week 24 is defined as:

- Sum of daily GC exposures (total daily dose multiplied by days on a regimen) from CM eCRF
- Sum of stress doses (HCe mg) (from CM eCRF where the indication for the stress dosing is “STRESS DOSE/DOSING”)

For subjects who discontinue study drug treatment prior to the Week 24 visit, the cumulative dose will be summed over the duration of Study Day 1 to the date of last dose of study drug.

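### As worded, the GC diary compliance formula counts a diary-recorded stress-dosing day twice, so the score can exceed 100% and slightly overstate adherence at the 80% Per-Protocol limit

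*SAP*

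**What the plan says.** SAP 8.3.19.5.3 defines the numerator of total GC diary compliance as the count of 'Yes' or 'Took Stress Dosing' "responses to taking GC as directed and number of stress dosing days". The denominator is LASTDAY – FIRSTDAY + 1, "where LASTDAY is the date of last dose, and FIRSTDAY is the date of first dose", so each calendar day enters it once. The section neither removes overlap between the terms nor caps the result at 100%.

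Four other places bear on how this should be read:

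- **Source of stress dosing.** SAP 8.3.20.4 looks first to "an entry in the diary indicating a stress dose was taken", and otherwise to "a record in the CM eCRF if the stress dosing was not recorded in the diary in a timely manner". SAP 11.2 names the daily diary as the source for stress-dosing summaries. SAP 4.2.3 has stress dosing recorded both by the subject in the diary and by the investigator on the eCRF.
- **What happens on a stress day.** Under Protocol 4.1.4.4 the stress dose replaces the usual dose, and usual GC "should be temporarily held during stress dosing and reinstated as soon as the stress dosing period ends".
- **Use of the score.** SAP 7.3 removes a subject from the Per-Protocol set when adherence to study drug or to the GC regimen, "determined by pill count and diary data compliance", is below 80%.
- **Onward use.** SAP 8.3.19.5.4 averages study drug, food and GC diary compliance with equal weight into a composite.

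**The concern.** A subject who records a stress day gives one diary response for it. That response is in the numerator through 'Took Stress Dosing', and the same day is then added again as a stress-dosing day. Because the stress dose replaces the usual dose, one response already accounts for the whole day's GC and nothing is left for a second credit to represent.

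The error only raises compliance. This matters at the 80% limit, because the diary formula is the only GC adherence formula in the SAP; the tablet-count formula in 8.3.19.1 is for study drug. A subject just under the limit could be kept in the Per-Protocol set because of the extra credit. Two programmers reading the sentence differently could also produce different Per-Protocol sets.

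**Working it through.** The plan gives no numerical result for this formula, so there is no figure to reproduce. The check is direct arithmetic.

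**Inputs**

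- Y = 'Yes' responses; S = 'Took Stress Dosing' responses; s = stress-dosing days (SAP 8.3.19.5.3).
- D = days from first to last dose. The double-blind part is 24 weeks, 24 × 7 = 168 days. The whole Treatment Period is 76 weeks, 76 × 7 = 532 days.
- Limit: 80% (SAP 7.3). With D = 168, 0.80 × 168 = 134.4, so 135 credited days are needed.
- One oral stress-dosing episode usually lasts 2 to 3 days (Protocol Table 2).
- Stress days per subject: not given. Assumed 2 to 6 over 24 weeks (one or two episodes), with 12 and 20 shown as a wider range.

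**Formulas**

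- As written: (Y + S + s)/D.
- Each day once: (Y + S)/D.
- If all stress days are in the diary, S = s and the difference is s/D.

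**Size per stress day**

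- 1/168 = 0.6 points; 1/532 = 0.19 points.

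**Inflation over 168 days, and the lowest once-counted compliance that still passes, (135 – s)/168**

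| s | Inflation s/168 (points) | Lowest once-counted compliance passing 80% |
|---|---|---|
| 2 | 1.2 | 133/168 = 79.2% |
| 3 | 1.8 | 132/168 = 78.6% |
| 6 | 3.6 | 129/168 = 76.8% |
| 12 | 7.1 | 123/168 = 73.2% |
| 20 | 11.9 | 115/168 = 68.5% |

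Over 532 days, s = 6 adds 6/532 = 1.1 points and s = 20 adds 20/532 = 3.8 points.

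**Illustrative subjects, D = 168**

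- Y = 162, s = 6, fully adherent: 168/168 = 100.0% counted once; 174/168 = 103.6% as written.
- Y = 128, s = 5: 133/168 = 79.2% counted once; 138/168 = 82.1% as written.
- Y = 120, s = 8: 128/168 = 76.2% counted once; 136/168 = 81.0% as written.

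The first is an impossible value for a proportion of days. The other two change side at 80%.

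**Composite score.** GC diary compliance has weight 1/3, so s = 6 over 168 days adds 3.6/3 = 1.2 points.

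**Weekly score.** SAP 8.3.19.5.4 sends weekly GC compliance to the study-drug weekly method, which counts responses over 7 with no added stress term. Whether the double count reaches the weekly measure is therefore unclear. If the 8.3.19.5.3 numerator were used, a week with 3 stress days, 2 'Yes' and 2 missed days would score (2 + 3 + 3)/7 = 114% instead of 5/7 = 71%.

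**The case against.** The best defence is that the added term was meant only for stress days found in the CM eCRF and absent from the diary. SAP 8.3.20.4 provides for that second source, and such days have no diary response, so adding them would double nothing. This is plausible as intent, but 8.3.19.5.3 does not state the restriction. Taking stress days from the eCRF without removing duplicates would not help either, because SAP 4.2.3 has the same episodes recorded in both places.

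A second defence is SAP 8.3.19.5, which resolves two diary entries on one date and so points to one entry per day as the intended unit. That rule deals with duplicate entries; it does not reach a separate term added to the count. Programming checks would probably notice values above 100%, but an inflated value below 100% gives no such signal.

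The limits on consequence stand. The stress-day frequency and the distribution of GC compliance are not in the documents, so the examples are hypothetical. SAP 7.3 applies the limit over the Treatment Period but also builds the set for each part of it, so the denominator could be 168 or 532 days, and the longer one shrinks the effect. Pill count is also named as a determinant and might exclude some of these subjects, although the SAP gives no GC pill-count formula and entrants under protocol version 7.0 or higher use investigator-prescribed GC.

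A reader might infer that stress dosing will differ between arms as GC is lowered, so that the error biases the comparison. The documents do not support this. Protocol 4.1.4.4 ties stress dosing to illness, surgery and trauma, and Protocol 7.1.5 treats adrenal insufficiency from undertreatment separately. Nothing shows that a lower daily dose brings more stress days.

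**Conclusion.** The defect holds as a matter of wording: read as written, the formula gives each diary-recorded stress day two credits against one day, and the score can exceed 100%.

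The practical effect is small. It rests on two assumptions: that stress days are recorded in the diary, and that a subject has one or two episodes of 2 to 3 days in 24 weeks. The inflation is then about 1 to 4 points over 168 days, and only subjects whose once-counted GC compliance falls within that distance below 80% could wrongly remain in the Per-Protocol set. More stress days would widen the band; the 532-day denominator would narrow it.

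A reader might infer that non-adherent subjects will enter the Per-Protocol set. The documents show only that this is possible, not that it will happen or to how many. The Per-Protocol analyses are supportive (SAP 7.3), and the primary analysis uses all randomized subjects and disregards GC non-compliance (SAP 12.3.1), so it is untouched. This is a minor correction worth making before the Per-Protocol set is fixed.

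**What to change.** Replace the numerator in SAP 8.3.19.5.3 with a count of calendar days, each counted at most once. A day is compliant if the diary response is 'Yes' or 'Took Stress Dosing', or if it has no diary entry and a CM eCRF stress-dose record covers it. The result then cannot exceed 100%.

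State in 8.3.19.5.4 that the same rule applies to the composite and weekly GC measures. In 7.3, say which denominator the 80% limit uses, since the size of any compliance error depends on it.

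The cost is a few lines of SAP text and the matching programming. No new data are needed, and the change preserves the purpose of the added term if it was meant for eCRF-only days.

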8.3.19.5.4 Composite Diary Compliance

Aggregate diary compliance is calculated as (study drug compliance + food compliance + GC diary compliance) divided by 3. Compliance versus each component (study drug, GC compliance and food compliance) will also be presented and summarized.

Weekly compliance for GCs and aggregate compliance is calculated using the same methodology as weekly study drug compliance.

8.3.20 Glucocorticoid Therapy

GC therapies are concomitant medications that fall under the Anatomical Therapeutical Chemical (ATC) classification is "Systemic Hormonal Preparations, Excl. Sex Hormones and Insulins" or "Glucocorticoids."

8.3.20.1 Duration (Days) on Current Background Glucocorticoid Therapy

Duration (days) on the Sponsor-provided or Principal Investigator-prescribed supply of standardized GC regimen is defined as the date of first dose of study drug (GC Conversion Period) - the date of start of the current background GC therapy + 1 day.

8.3.20.2 Glucocorticoid Dose in Hydrocortisone Equivalents

[Table 11](#) defines the potencies of various GCs relative to HC in treating CAH. These conversion factors will be used to determine whether a subject's daily GC dose satisfies study eligibility criteria and provide general guidelines for GC tapering.

Table 11 Relative Potencies of Glucocorticoids in Hydrocortisone Equivalents

Glucocorticoid	Potency in CAH (HCe)
Hydrocortisone	1
Prednisone	4
Prednisolone, Prednisolone Sodium Phosphate, Methylprednisolone	5
Fludrocortisone	0
Dexamethasone	70
Cortisone Acetate	0.8

8.3.20.3 Glucocorticoid Total Daily Dose in Hydrocortisone Equivalents

The total daily GC dose of a given subject is calculated as the sum of doses per day of concomitant GC therapies using the conversion in [Table 11](#), excluding stress dosing.

8.3.20.4 Stress Event

A stress event is defined as an entry in the diary indicating a stress dose was taken or a record in the CM eCRF if the stress dosing was not recorded in the diary in a timely manner. Consecutive days of stress dosing are counted as a single stress event.

8.3.20.5 Cumulative GC Dose at Week 24

The cumulative GC dose from Study Day 1 to Week 24 is defined as:

- Sum of daily GC exposures (total daily dose multiplied by days on a regimen) from CM eCRF
- Sum of stress doses (HCe mg) (from CM eCRF where the indication for the stress dosing is “STRESS DOSE/DOSING”)

For subjects who discontinue study drug treatment prior to the Week 24 visit, the cumulative dose will be summed over the duration of Study Day 1 to the date of last dose of study drug.

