5.1.3 Exploratory Efficacy Endpoints

5.1.3.1 Percent Change in HCe Dose at Week 24

Exploratory Efficacy Endpoint 3.1 evaluates the effect of randomized treatment in reducing GC HCe dose in classic CAH subjects at Week 24 in mean percentage terms. This analysis will be achieved by examination of the change in daily GC HCe dose from baseline (Day 1) to post baseline visits on the log scale. Results will be back transformed to present the outcome as a percentage change.

5.1.3.2 Cumulative HCe Dose at Week 24

Exploratory Efficacy Endpoint 3.2 evaluates the effect of randomized treatment in reducing the cumulative HCe dose (total exposure in HCe mg) in classic CAH subjects over 24 Weeks. The endpoint is the cumulative GC dose in HCe from baseline (Day 1) at Week 24. Similar to endpoint 3.1, the endpoint will be analyzed on the log scale.

5.1.3.3 Change in HOMA-IR at Weeks 24 and 52

Exploratory Efficacy Endpoints 3.3 and 3.4 evaluate the effect of randomized treatment in improving HOMA-IR in classic CAH subjects at Weeks 24 and 52. The associated endpoints are the change in fasting HOMA-IR from baseline (Day 1) to Week 24 and Week 52.

5.1.3.4 Improving Cardiovascular Risk Factors at Week 52

Exploratory Efficacy Endpoint 3.5 evaluates the effect of randomized treatment in reducing CV risk factors in classic CAH subjects at Week 52. The endpoint is similar to Secondary Efficacy Endpoint 2.3, being the proportion of subjects who had improvement in at least one CV risk factor at Week 52. Only subjects CV risk factors at baseline will be included in the endpoint analysis.

5.1.3.5 GC use while maintaining androgen control at Week 52

Exploratory Efficacy Endpoints 3.6 and 3.7 are similar to the Secondary Efficacy Endpoints 2.1 and 2.2, but now assessed at 52 weeks. Secondary Efficacy Endpoints 3.6 is the response to randomized treatment in terms of reducing GC to $\leq 11\text{mg mg/m}^2/\text{day}$ in HCe while maintaining

androgen control, defined as A4 levels at approximately baseline ($\leq 1.2x$ baseline) or within normal limits (\leq ULN) at Week 52 in subjects with CAH.

Exploratory Efficacy Endpoint 3.7 is similar to 3.6 but evaluated in those subjects with baseline GC ≤ 35 mg/m²/day in HCe.

5.1.3.6 Quality of Life at Week 24 and Week 52

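### Cumulative GC dose (SAP 8.3.20.5, exploratory endpoint 3.2) adds stress doses without removing the usual dose that the protocol says they replace, so it can be over-counted by up to one usual daily dose per stress day

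*SAP*

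**What the plan says.** **SAP.** Section 8.3.20.5 builds cumulative dose from two terms, both taken from the CM eCRF. The first is "Sum of daily GC exposures (total daily dose multiplied by days on a regimen) from CM eCRF". The second begins "Sum of stress doses (HCe mg" and is limited to records whose indication is stress dosing. Nothing is subtracted for stress days. Section 8.3.20.3 leaves stress dosing out of the total daily dose. Section 5.1.3.2 describes the target of endpoint 3.2 as "cumulative HCe dose (total exposure in HCe mg) in classic CAH subjects over 24 Weeks". Section 12.6.4 analyses its logarithm by ANCOVA and also reports geometric means, quartiles and extremes.

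**Protocol.** Section 4.1.4.4 says the Table 2 stress doses replace the usual daily dose and are not additional to it. For oral stress dosing, "the subject should take the entire stress dose using HC tablets from the bottle provided by the Sponsor". Usual "GCs should be temporarily held during stress dosing and reinstated as soon as the stress dosing period ends". On recording, every stress dose is to be entered, but "changes to usual daily GC dose only need to be entered into EDC when there is a definitive long-term, chronic alteration". The usual home-management entry in Table 2 reads "Approximately double the routine oral GC dose (and give as HC) until recovery (usually 2 to 3 days").

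**The concern.** The protocol treats stress dosing as a substitution; the SAP formula treats it as an addition. A subject who follows the protocol takes no usual dose on a full stress day. The recording rule gives the site no reason to break the regimen record for a hold of two or three days. That day then contributes the usual dose through the first term and the whole stress dose through the second.

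Two provisions that might be expected to prevent this do not. Section 8.3.20.3 stops the stress dose entering the daily total, but it does not set the usual dose to zero on a stress day. The reconciliation across eCRFs in SAP 4.3.1.2 is general and does not mention held doses.

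At stake is whether endpoint 3.2 measures total exposure, both in its reported levels and, under some patterns of stress dosing, in the between-arm ratio.

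**Working it through.** The plan states no cumulative dose, so there is no figure to reproduce. The check compares the formula with the dose taken under Protocol 4.1.4.4.

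**Inputs**
- From the documents: 24 weeks = 168 days; entry dose 30 to 60 mg/day in hydrocortisone equivalents (HCe); algorithm floor 15 mg/day; double dose for usually 2 to 3 days; triple dose for fever above 39 °C, rounded up to the next 10 mg tablet.
- Assumed: a usual dose of 35 mg/day for illustration, the taper below, and all stress-day counts beyond one 2 to 3 day episode. The documents give no stress-day counts.

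**Formula.** Let U be the usual daily dose, s the number of full stress days and m the stress multiple.
- SAP: 168U + s·m·U
- Taken: (168 − s)U + s·m·U
- Difference: s·U, whatever the stress dose

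**One episode at a constant 35 mg/day** (168 × 35 = 5,880 mg)

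| Case | Taken (mg) | SAP formula (mg) | Over-count |
|---|---|---|---|
| 2 days doubled | 166×35 + 140 = 5,950 | 6,020 | +1.18% |
| 3 days doubled | 165×35 + 210 = 5,985 | 6,090 | +1.75% |
| 2 days doubled, half the usual dose taken on day 1 | 5,967.5 | 6,020 | +0.88% |
| 3 days doubled, half the usual dose taken on day 1 | 6,002.5 | 6,090 | +1.46% |
| 2 days at 110 mg (tripled, rounded up) | 6,030 | 6,100 | +1.16% |
| 3 days at 110 mg (tripled, rounded up) | 6,105 | 6,210 | +1.72% |

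With exact doubling the percentage does not depend on U: at 30 mg/day, 5,130 v 5,220 mg is also +1.75%.

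**Arm level.** Subjects without stress dosing contribute no error. If half of an arm had one 3-day doubled episode (assumed), the geometric mean rises by √1.0175 − 1, about 0.9%.

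**Ratio, equal stress days.** Assumed taper with steps at Weeks 2, 8, 14 and 20: 35×14 + 30×42 + 25×42 + 20×42 + 15×28 = 4,060 mg, a mean of 24.17 mg/day. The comparison arm stays at 35 mg/day, and each arm has 3 doubled days.

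| Where the taper arm's stress days fall | Taken (mg) | SAP (mg) | Over-count | Ratio, taken | Ratio, SAP | Shift |
|---|---|---|---|---|---|---|
| Spread evenly | 4,132.5 | 4,205 | +1.75% | 0.6905 | 0.6905 | about 0 |
| All at 35 mg | 4,165 | 4,270 | +2.52% | 0.6959 | 0.7011 | +0.75% |
| All at 15 mg | 4,105 | 4,150 | +1.10% | 0.6859 | 0.6814 | −0.65% |

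The last two rows are extremes: every subject's stress days would have to fall at the same end of the taper.

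**Ratio, unequal stress days at a constant 35 mg/day.** For 6 v 3 doubled days, taken is 6,090/5,985 = 1.0175 and the SAP formula gives 6,300/6,090 = 1.0345, a shift of 1.7%. For 3 v 2 days the shift is 0.6%.

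**The case against.** The strongest objection is that the over-count is not established. The CRFs are not in the documents. The error is zero if the site recorded the hold, if the subject took both doses, or if the CM eCRF holds only the increment over the usual dose. The SAP does not define days on a regimen, and a regimen that is held could be read as one the subject is not on. The recording rule does not forbid entering a hold, and the protocol lets sites vary the stress-dosing guidelines. All of this stands and makes the point conditional. It does not remove it: no text tells the programmer to leave out held days, and the recording rule points towards full stress-dose entries beside an unbroken regimen record.

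The second objection is size. The percentages apply to an affected subject, not an arm, and stress days spread evenly over the taper leave the ratio where it was. This stands too.

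A reader might infer that endpoint 3.2 is certainly inflated, or that the treatment comparison is biased whenever usual dose falls during the trial. The documents support neither. The first depends on CRF content that cannot be seen. The second needs stress days that differ between arms or cluster at high or low usual doses.

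**Conclusion.** A minor defect in a derivation rule. As written, SAP 8.3.20.5 does not compute the exposure described in 5.1.3.2 if the CM eCRF holds full stress doses and the regimen record is unbroken. The over-count is then up to one usual daily dose per stress day: about +1.2% to +1.75% for a subject with one typical doubled episode, smaller where part of the usual dose was taken first, and diluted at arm level.

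The between-arm ratio is about unchanged when stress days are balanced and evenly spread. It shifts by 1.7% for an assumed 3 v 6 days, and by +0.75% or −0.65% at the assumed extremes of clustering.

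Endpoint 3.2 is exploratory and outside the type I error control in SAP 9.6. The primary and secondary endpoints do not use cumulative dose and are unaffected. Confidence is medium, because the deciding fact is in CRFs that are not available.

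**What to change.** 1. Confirm whether the CM eCRF stress record holds the full dose or only the increment. If only the increment, keep the formula.
2. If it holds the full dose, state in 8.3.20.5 that the usual dose is excluded only for days with a CM eCRF stress dose in mg, except where records show that the usual dose was also taken.
3. Query stress days that appear only in the diary. If they stay unresolved, keep the usual dose for those days. SAP 8.3.20.4 identifies a stress event from the diary, "or a record in the CM eCRF if the stress dosing was not recorded in the diary in a timely manner", but the diary items listed in Protocol 8.3.8 include dates and no dose. Excluding diary-only days would remove the usual dose and add nothing. For three doubled days at 35 mg/day the true total is 5,985 mg; that rule gives 5,775 mg (−3.5%), worse than the present formula's 5,880 mg (−1.75%).
4. State how part-days at the start of an episode are counted, and report the present formula as the upper bound for days with a recorded stress dose.

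The completer analysis in SAP 12.6.4.1 inherits the corrected definition.

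**Cost.** One rule, a date join between records already collected, and some queries. The result relies on complete stress-dose dates. Excluding whole days brings a small downward bias on part-days: if half of a 35 mg dose was taken first, 5,985 v 6,002.5 mg, or −0.3%.
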